### Tertiary objectives

- To assess if early DD injection therapy represents good value for money compared to current clinical care.
- To determine circulating levels of adalimumab and antibodies to adalimumab in the blood.

### Exploratory objective

To investigate changes in other molecule markers relevant to the progression of DD.

## 3. STUDY METHODS

### 3.1 Trial Design/framework

The RIDD trial is designed as a **randomised, multi-centre, double blind, placebo-controlled, parallel group, phase II trial to determine the efficacy of intra-nodular injection of anti-TNF in delaying disease progression in early DD when compared to a saline placebo**. The study will be performed across at least 3 participating centres. **Intra-nodular injection of anti-TNF will be performed at baseline, 3, 6 and 9 months**. Primary comparison will be performed using a measure of **change in nodule hardness from baseline**, assessed at the **primary endpoint of 12 months**, with secondary analysis comparisons of this measure further taking into account the **co-endpoints of 3, 6, 9 and 18 months after first treatment**. Secondary outcome analyses will also be performed analysing observed differences on **ultrasound imaging of nodule size, range of motion of the affected digit, grip strength, Michigan Hand Outcomes Questionnaire score, participant identified activity most restricted by DD (scored on a scale of 1-10), injection experience, progression to surgery and adverse events within the first 18 months after initial treatment between the trial treatment groups**.

Grant activation:	01Mar2015
Trial Open (start of recruitment) for Part 2:	08Jan2017
First DSMC meeting (actual):	22Mar2017
End of recruitment:	31Dec2018 (UK) 12Apr2019 (Netherlands)
Date expected end follow-up/start of data cleaning:	06Dec2020 (UK) 04Jan2021 (Netherlands)
Expected start of final analysis:	26Jan2021
End of grant:	30Jun2021

Repurposing anti-TNF for treating Dupuytren's disease (funded by Health Innovation Challenge Fund, Wellcome Trust)  
EudraCT Number: 2015-001780-40 and OCTRU Reference Number CTU0028

### 3.2 Randomisation and Blinding

Randomisation will be undertaken at or prior to the baseline visit prior to receiving the trial injection. Participants will be randomised 1:1 to placebo or adalimumab with stratification by age and centre. Participants will be randomised through a secure online service provided by the Oxford Clinical Trials Research Unit (OCTRUE) called RRAMP. RRAMP is used to randomise participants and this will generate a Trial ID and prompt an email to Pharmacy which informs them of which IMP (drug or placebo) to dispense.

Full details of the randomisation are available in **RIDD\_RBP\_v9.0\_18May2018**, stored in the confidential statistical section of the TMF.

The methods for blinding will be influenced by the packaging of the adalimumab being used. For part 2, pre-filled syringe is the only option for using the 40mg in 0.4ml formulation. Due to the distinctive appearance of the syringe, it is not possible to blind the healthcare professional administering the injection to treatment allocation. To protect the quality of the data, any person injecting with a pre-filled syringe will NOT be involved in administering any further trial procedures. Any healthcare professionals involved with administering any trial procedure, including outcome assessments, after the injection of IMP will be blinded to treatment.

The IMP (which will be stored in pharmacy) will be dispensed with accountability to a member of the research team who will take the IMP to a clinic room separate from the participant. Care will be taken to ensure any healthcare professionals blinded to treatment allocation are not present for the injection, and the syringe will be hidden from the participant's view.

In summary, participants and healthcare professionals involved in participant follow-up and outcome assessment will always be blinded to treatment allocation. Laboratory staff will be blinded to treatment allocation.

### 3.3 Sample Size

The sample size is based on unpublished data acquired in a pilot study 'Ultrasonographic (grey scale) characteristics of DD and their relationship to the clinical features and functional severity of the disease: a pilot study' (REC Ref. 11/SC/0447). Within the study there were 25 participants with mean nodule hardness of  $53 \pm 8$  for participants suffering DD and  $32 \pm 3$  for corresponding controls matched by age and sex.

Using the study, a minimum of 138 participants (69 per arm) would be required to detect a moderate effect size of 0.62, based on a 5 point change in nodule hardness at 12 months and assuming a standard deviation of 8 (5% significance (2-sided) and 90% power, allowing for a 20% loss to follow up).

### 3.4 Statistical Interim Analysis, Data Review and Stopping guidelines

#### *Interim analysis*

There are no formal interim analyses of the outcomes planned for RIDD part 2 but these will be conducted at the request of the Data and Safety Monitoring Committee (DSMC).

#### *Details of the Data Safety and Monitoring Committee remit*

The role of the DSMC is to safeguard the interests of trial participants, monitor the main outcome measures including safety and efficacy, and monitor data quality and completeness. The DSMC will undertake interim review of the trial's progress including updated figures on recruitment, data quality, adherence to protocol and follow-up, and main outcomes and safety data. The DSMC will first meet before the trial starts and within

Repurposing anti-TNF for treating Dupuytren's disease (funded by Health Innovation Challenge Fund, Wellcome Trust)

EudraCT Number: 2015-001780-40 and OCTRU Reference Number CTU0028

one year of recruitment commencing. Full details regarding DSMC remit are present in the RIDD DSMC Charter ([RIDD\\_DSMCCharter\\_V1.0\\_15Sep2017.docx](#)).

#### *Stopping guidelines*

Formal statistical methods are more generally used as “stopping” guidelines rather than absolute rules. This is because they generally only consider one dimension of the trial. Reasons should be recorded for disregarding a stopping guideline. The statistical guidelines for the trial are described in outline in the protocol and in detail in the Outline Statistical Analysis Plan.

In the light of interim data, and other evidence from relevant studies (including updated overviews of the relevant randomised controlled trials), the DSMC will inform the TSC, if in their view there is proof beyond reasonable doubt that the data indicate that any part of the protocol under investigation is either clearly indicated or contra-indicated for a particular subgroup of trial participants. A decision to inform the TSC will in part be based on statistical considerations. Appropriate criteria for proof beyond reasonable doubt cannot be specified precisely. A difference of at least 3 standard errors in the interim analysis of a major endpoint may be needed to justify halting, or modifying, such a study prematurely.

### **3.5 Timing of Final Analysis**

**Table 1:** Objectives, outcome measures, and time points of evaluation

Outcome Measures	Time point(s) of evaluation of this outcome measure					
	Baseline	3 month a	6 month b	9 month b	12 month b, c	18 month b, c
Primary objective						
To determine if injection with adalimumab is superior to placebo injection of normal saline in controlling disease progression in participants with early Dupuytren's disease (DD)	Change in hardness of selected nodule for participants between baseline and 12 months after first treatment					*
Secondary objectives						
To determine if injection with adalimumab is superior to placebo injection of normal saline in controlling disease progression in participants with early DD	Change in hardness of selected nodule for participants on each treatment at baseline, 3, 6, 9, 12 d and 18 months after first treatment	*	*	*	*	*
	Ultrasound imaging of nodule size	*	*	*	*	*
To compare the development of DD nodules and associated cord, flexion deformities of the fingers and	Range of motion of the affected digit	*	*	*	*	*
	Grip strength	*	*	*	*	*

Repurposing anti-TNF for treating Dupuytren's disease (funded by Health Innovation Challenge Fund, Wellcome Trust)  
EudraCT Number: 2015-001780-40 and OCTRU Reference Number CTU0028

Outcome Measures	Time point(s) of evaluation of this outcome measure					
	Baseline	3 month a	6 month b	9 month b	12 month b, c	18 month b, c
impairment of hand function for participants on each treatment						
Michigan Hand Outcomes Questionnaire (MHQ)	*	*	*	*	*	*
Participant identified activity most restricted by DD score on a scale of 1-10		*	*	*	*	*
Progression to surgery of the digit being assessed						*
To assess acceptability of injections to patients						
Injection experience	*	*	*	*		
Monitor for adverse events						
Adverse event monitoring comparing active and placebo groups using visual inspection of injection site	*	*	*	*	*	
Tertiary objectives						
To assess if early DD injection therapy represents good value for money compared to current clinical care e						
Analysis of EQ-5D-5L data to estimate utilities using quality-adjusted life years (QALYs) from participants on each treatment	*	*	*	*	*	*
Analysis of resource use data to estimate the cost of each treatment		*	*	*	*	*
To monitor circulating levels of adalimumab and antibodies to adalimumab in the blood						
Monitor circulating levels of adalimumab and antibodies to adalimumab in the blood	*	*				*
Exploratory objective						
To investigate changes in other molecular markers relevant to the progression of DD e						
Change in level of the markers	*	*				*

a ± 2 weeks | b ± 4 weeks | c where participants' 12- or 18-month data collection was delayed due to SARS-CoV-2 pandemic, the outcomes recorded via questionnaires should be completed within ± 4 weeks and the physical measurements should be completed within ± 3 months, where it is safe to do so, with additional questionnaires completed at the point of delayed physical outcomes measurement | d the nodule hardness secondary objective will account for all timepoints where this information has been collected, including the primary end-point of 12 months | e analysed by health economist

Repurposing anti-TNF for treating Dupuytren's disease (funded by Health Innovation Challenge Fund, Wellcome Trust)  
EudraCT Number: 2015-001780-40 and OCTRU Reference Number CTU0028

### 3.6 Blinded analysis

A blinded analysis of data (data analysed with no treatment information added) will be undertaken prior to the final data lock in order to clarify whether continuous variables are normally distributed and to identify participants who will be excluded from the per-protocol analysis.

Primary outcome measurements were conducted using two validated portable durometers. Following identification of potential issues with the initial study device with nodule hardness recording in patients with marked distortion of the skin close to their DD nodule, a second device which would not be affected by such distortions, was sourced and utilised. Patients in two study centres (Oxford and Edinburgh) had all subsequent measurements taken using both devices and patients in one study centre (Groningen) had all of their study measurements recorded using the newer device only. During the blinded analysis the results from the two durometers will be compared using a Bland-Altman plot. A cross-walk methodology will be used to map the results from the old tonometer to the results of the new tonometer, to allow maximum data utilisation. If this cross-walk is not effective in mapping the tonometer results, alternative measures may include favouring the results from the new device and using the results from the original device only where data for the new device are not available.

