### 3.7 Statistical Analysis Outline

In the RCT (**Part 2**), all analyses will be performed on participants randomised to **Part 2** only, on an intention-to-treat basis with sensitivity analyses run on the per protocol population.

The primary outcome measure is change in nodule hardness from baseline to 12 months. There will only be one dose level used in **Part 2**, which will be 40mg of adalimumab. It is expected that all nodules will be large enough to accommodate the injection, but if not the volume of residual IMP will be recorded. The difference in the mean change of nodule hardness between the two groups will be reported with 95% confidence intervals. The comparison of change in nodule hardness between interventions will be analysed primarily using Analysis of Covariance (ANCOVA) adjusting for baseline, if it is normally distributed. As a secondary confirmatory analysis, ANCOVA adjusting for baseline nodule hardness as well as the stratification factors comprising centre (Oxford, Edinburgh or Groningen) and age (as a continuous variable) will be conducted.

If the data are not normally distributed, the data will be log-transformed in order to gain normality and geometric means with 95% confidence intervals will be reported. If data are not normally distributed after log-transformation, the non-parametric Mann Whitney test will be used with no adjustment for baseline, and the median change with 95% confidence intervals will be reported.

In order to analyse change in nodule hardness over the full time period, linear mixed effects regression will be used to compare nodule hardness between interventions utilising all time-points up to 18 months and adjusting for stratification and other important prognostic factors.

The secondary outcome measures for **Part 2** include those for **Part 1** and also grip strength, range of motion and participant reported outcomes.

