## 6. ANALYSIS

### 6.1 Outcome Definitions

#### Primary outcome

Nodule hardness from baseline to 12 months: The primary outcome is hardness of nodule selected for treatment measured at 12 months post-first injection using a validated portable durometer. During the initial stages of this study researchers within the team noted that the original portable durometer being used to measure nodule hardness in the UK-based centres was potentially unable to achieve accurate measurements in patients with moderate to severe deformities of their hands due to their DD. Following this an alternative durometer with a longer probe, which would be able to overcome this issue, was sourced. To ensure patients who had nodule hardness data collected using only the original durometer were not excluded from analyses, or included with inaccurate data, all subsequent patients recruited in the UK-based centres had their nodule hardness data collected with both the original and the new portable durometer. The centre in the Netherlands only recorded data using the newer portable durometer.

The outcomes for RIDD were tested in our ultrasound study (REC Ref. 11/SC/0047) 'Ultrasonographic (grey scale) characteristics of DD and their relationship to the clinical features and functional severity of the disease: a pilot study'. Preliminary (unpublished) tonometry data from 25 patients in this trial demonstrated that the

Repurposing anti-TNF for treating Dupuytren's disease (funded by Health Innovation Challenge Fund, Wellcome Trust)

EudraCT Number: 2015-001780-40 and OCTRU Reference Number CTU0028

palmar tissue of patients with untreated DD were significantly firmer than the corresponding age and sex matched controls.

Using the measurements from the portable durometers, the amount of indentation is converted to hardness reading on a scale with 100 units (internationally standardised durometer units). The time window for collecting the primary end-point nodule hardness data will allow  $\pm$  4 weeks to confer some flexibility. This will be extended to  $\pm$  3 months where physical measurements could not be safely recorded due to the SARS-CoV-2 pandemic.

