## 6.2 Analysis methods: Primary outcome

The primary outcome analysis will be performed on the ITT population, comparing intervention (adalimumab) against placebo (saline, 0.9% NaCl) for all randomised participants with available nodule hardness data.

The adjusted difference in the mean change of nodule hardness between the two groups will be reported with 95% confidence intervals. The primary time point is 12 months. The primary analysis will be the comparison of change in nodule hardness between the adalimumab and saline groups using Analysis of Covariance (ANCOVA) adjusting for baseline nodule hardness, if it is normally distributed. If the data are not normally distributed, the data will be log-transformed in order to gain normality and geometric means with 95% confidence intervals reported. If data are not normally distributed after log-transformation, the non-parametric Mann-Whitney test will be used with no adjustment for baseline, and the median change with 95% confidence intervals will be reported.

As a supporting analysis, ANCOVA adjusting for baseline nodule hardness as well as the stratification factors comprising centre (Oxford, Edinburgh or Groningen) and age (as a continuous variable) will be conducted.

As a further supporting analysis, in order to analyse change in nodule hardness over the full time period, linear mixed effects regression will be used to compare nodule hardness between interventions utilising all available time-points up to 18 months and adjusting for stratification factors. Multilevel models permit all available data to be included in the analysis, thus eliminating complete case bias.

**Appendix 5: Outcome measure summaries, Table 8:** Mean (with SD) nodule hardness recorded at each study time-point.

**Appendix 5: Outcome measure summaries, Table 9:** Mean (with SD) nodule hardness at 12 months by number of injections received.

**Appendix 5: Outcome measures analysis, Table 17:** Nodule hardness ANCOVA and linear mixed-effects regression results for all follow-up time-points.

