## 6.5 Pre-specified Subgroup Analysis

### Primary outcome

Subgroup analyses to examine the role of age group, location of treating centre, known family history of DD, and alcohol intake upon the effect of the primary outcome (nodule hardness at 12-months post-first injection) will be performed. This analysis will be carried out using adjusted ANCOVA, including age and centre. For these analyses, age will be categorised into two groups of 18 to 49 years and 50 years or older, and alcohol intake will be categorised into four groups of non-drinker, up to 14 units/week, 14 to 35 units/week and more than 35 units per week. Treating centre location will also be categorised into two groups, defined as UK-based centres (Oxford and Edinburgh) and non-UK based centres (Groningen). Comparisons will be using a 2-sided significance level of 5% and 95% confidence intervals, and results will be tabulated as per the primary outcome adjusted ANCOVA and presented by strata using Forest plots.

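### If the durometer cross-walk fails, the fallback can pair an original-device baseline with a new-device 12-month reading, and the primary ANCOVA has no device term

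*SAP*

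**What the plan says.** SAP 3.6 explains that a second durometer was brought in during the study because the first could misread where the skin near the nodule was distorted. After that, Oxford and Edinburgh patients "had all subsequent measurements taken using both devices", while Groningen used the newer device throughout. The plan is a Bland-Altman comparison in blinded review, and then: "A cross-walk methodology will be used to map the results from the old tonometer to the results of the new tonometer". If the mapping is not effective, the alternatives the SAP may adopt include favouring the new device and "using the results from the original device only where data for the new device are not available".

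SAP 6.1 describes the dual readings differently: "all subsequent patients recruited in the UK-based centres had their nodule hardness data collected with both the original and the new portable durometer". It also refers to patients who have original-device data only.

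On the analysis, SAP 3.7 states: "The primary outcome measure is change in nodule hardness from baseline to 12 months". SAP 6.2 analyses this "using Analysis of Covariance (ANCOVA) adjusting for baseline nodule hardness, if it is normally distributed". If normality fails even after log-transformation, "the non-parametric Mann-Whitney test will be used with no adjustment for baseline". The supporting ANCOVA adds centre and age, and the mixed model adds the stratification factors. Neither has a device term. No device analysis appears among the sensitivity analyses in 6.2.2, in the Covid-19 list in 15.1, or in the sensitivity headings of the table appendix.

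**The concern.** On the wording of 3.6, a UK participant enrolled before the change and seen at 12 months after it has an original-only baseline and both readings at 12 months. A rule that takes the new device wherever it exists then subtracts an original-device baseline from a new-device 12-month value, although an original-device value exists at both visits. The fallback is reached only when the difference between devices could not be mapped satisfactorily, so this is when mixing matters most.

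Nothing later in the analysis removes the offset. Centre cannot separate participants enrolled before and after the change within Oxford or Edinburgh. Two things are at stake: the precision of the primary comparison, and the meaning of the mean change reported for each arm, part of which could be a change of instrument.

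**Working it through.** **The plan's own figure.** Inputs from SAP 3.3: difference 5, SD 8, two-sided 5%, power 90%, 20% loss.
- n per arm = 2 × (1.960 + 1.282)² × 64 / 25 = 54; 54 / 0.8 gives 68, so 136 in total.
- With the rounded effect size 0.62: 55 per arm; 55 / 0.8 gives 69, so 138 in total, as stated.
- I use 55 evaluable per arm below.

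**Can a mixed pair arise?** It depends on which section is right.
- On 3.6 (later measurements dual): participants enrolled before the change are original-only at baseline and dual at 12 months. The fallback, applied reading by reading, gives original then new.
- On 6.1 (later recruits dual): early participants are original at both visits and later ones new at both. Mixed pairs largely disappear.

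**Assumptions, since the documents give no values.** A constant device offset D; a share q of participants with a mixed pair, independent of arm; SD 8 at both visits; correlation r between baseline and 12 months. I take D = 5 with q = 0.25 and D = 10 with q = 0.50, each at r = 0.5 and 0.7.

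**Formulas.**
- Observed baseline variance = 64 + q(1−q)D²
- ANCOVA residual variance = 64 × [1 − r² × 64 / (64 + q(1−q)D²)]
- Variance of unadjusted change = 128(1−r) + q(1−q)D²
- Shift in within-arm mean change = qD (sign unknown)

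| | D = 5, q = 0.25 | D = 10, q = 0.50 |
|---|---|---|
| q(1−q)D² | 4.69 | 25 |
| Baseline variance (64 without mixing) | 68.69 | 89 |
| ANCOVA residual variance, r = 0.5 (48.0 without mixing) | 49.1 (+2%) | 52.5 (+9%) |
| ANCOVA residual variance, r = 0.7 (32.6 without mixing) | 34.8 (+7%) | 41.4 (+27%) |
| Change variance, r = 0.5 (64.0 without mixing) | 68.7 (+7%) | 89.0 (+39%) |
| Change variance, r = 0.7 (38.4 without mixing) | 43.1 (+12%) | 63.4 (+65%) |
| Shift in mean change | 1.25 | 5 |

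**Simulation check.** 4,000 trials, 55 per arm, r = 0.5, true effect −5. The ANCOVA estimate with mixed pairs stays at about −5.0 in both scenarios. Its standard error goes from 1.32 to 1.34 (D = 5, q = 0.25) and from 1.34 to 1.40 (D = 10, q = 0.50), in line with +2% and +9% in variance.

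**Power at 55 per arm,** from Φ(5 / (SD × √(2/55)) − 1.96):
- Unadjusted change at r = 0.5, a normal approximation to what the Mann-Whitney route would face: 90.6% without mixing (SD 8), 88.6% (SD 8.29), 79.4% (SD 9.43).
- ANCOVA at D = 10, q = 0.50: about 95% at r = 0.5 (residual SD 7.25) and about 98% at r = 0.7 (residual SD 6.44).

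**Chance imbalance.** A difference of 10 percentage points between arms in the share of mixed pairs moves the unadjusted between-arm difference by 0.1D, that is 0.5 units at D = 5 and 1.0 at D = 10.

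**The case against.** The case for leaving the text alone is substantial.

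- The fallback is doubly conditional. It applies only if the cross-walk is not effective, and even then it is something the SAP may do. The choice is made in blinded review before data lock. This stands, although the SAP sets no criterion for an effective cross-walk.
- The SAP does not say whether a new-device result must be unavailable for the reading or for the participant. A per-participant rule would create no mixed pairs. On the wording of 6.1 there would be few in any case. This stands, and is a reason to settle the text.
- The upper scenario is extreme. SAP 6.1 places the device problem in the initial stages of the study, and Groningen and later UK recruits contribute no mixed pairs, so a share of one half is unlikely. The +27% also needs a correlation of 0.7.
- Planning used SD 8 without credit for baseline adjustment, so ANCOVA power stays above 90% even in that scenario.
- The preference for the new device has a stated reason. Forcing original-device pairs into the primary analysis would rely on the instrument suspected of misreading. This stands, and it is why same-device pairing belongs in a sensitivity analysis.

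Three stronger readings are tempting but not supported. A reader might infer that the treatment effect is biased. Device history is fixed by enrolment date and centre, not by arm, so only chance imbalance remains. A reader might set the 5-unit shift against the 5-point planning effect, but the first is a within-arm mean and the second a between-arm difference. A reader might also conclude that the UK versus Netherlands subgroup in 6.5 is confounded with device. A constant offset cancels from the treatment contrast within each location. Only a difference in scale or reliability between devices would matter, and the documents give no figure for one.

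**Conclusion.** The point holds in a limited form. If the cross-walk is abandoned and the named fallback is applied reading by reading, 3.6 permits mixed-device change scores that no planned model or sensitivity analysis accounts for. The consequence is lost precision and a less interpretable mean change in each arm. It does not bias the superiority test.

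Over the assumed range, the loss in the primary ANCOVA runs from negligible (2%) to moderate (27%). It is larger on the unadjusted Mann-Whitney route, where power at r = 0.5 could fall to 79.4%. All of this rests on assumed offsets, shares and correlations and on a constant offset. The documents tie the device problem to hand deformity, so the true difference may vary between patients. The figures say nothing about the cross-walk itself. This is a cheap improvement to make before data lock, not a threat to the trial's conclusion.

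**What to change.** 1. State in SAP 3.6 that, if the fallback is used, the primary ANCOVA will include a device-pair indicator (original-original, original-new, new-new) and the mixed model a device term for each reading. With a constant offset, the indicator removes the added noise.
2. Add a sensitivity analysis restricted to same-device pairs: new-new where available, otherwise original-original. These readings should not be cross-walked, because the fallback applies only once the cross-walk has failed.
3. Reconcile 3.6 with 6.1 on whether participants already enrolled at the change were measured with both devices.

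The cost is SAP wording and one model term (two degrees of freedom if all three pair types occur). No new data are needed. The drawback is that the sensitivity analysis relies partly on original-device readings, which may be inaccurate in deformed hands, and this should be said when it is reported.
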